The third recruitment strategy consists of using a Qualtrics panel. According to Qualtrics, "A market research panel, also known as an online sample, is a group of people recruited to respond to a survey. They are typically chosen from a prearranged pool of respondents who've agreed to be contacted by a market research service in order to respond to surveys." Employing the study inclusion/exclusion criteria, Qualtrics panel, recruits willing participants for study participation. Participants recruited via the Qualtrics panel will be compensated directly via Qualtrics. They will receive a \$50 gift card for their participation.

Across all forms of recruitment, study conditions will be randomly assigned via the Qualtrics system. Once a participant provides consent and is screened for study inclusion, participants will complete the pre-test questionnaire. After completing the pre-test questionnaire, respondents will be assigned to one of two study conditions. They will either be asked to view one of the following: a brochure on safe disclosure or the 90 DAYS film. Upon completing one of the interventions, participants will be asked to immediately complete the post-test questionnaire. For participants recruited outside of the Qualtrics Panel, once all anonymous responses are submitted, they will be directed to a separate link to enter their randomized generated code and email address. The purpose of the randomized code is to verify that the participant completed the study. The purpose of the email address for those currently enrolled is two-fold. Firstly, it will allow researchers to compensate participants with a virtual \$30 Amazon gift card. Secondly, it will allow researchers to provide a follow up email, within 3-4 weeks, containing the link to the second

Version 10.5.2018 Page 4 of 11

post-test survey. Participants will be compensated with a \$20 virtual Amazon gift card. Altogether, currently enrolled respondents in the main study (N = 3), will receive a total of \$50 for their participation in the study. After each data collection, participants will be reminded of their right to withdraw their responses from the study without penalty.

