For newly enrolled participants, whether recruited via Qualtrics, social-media, health agencies, or word-of-mouth, only one wave of data collection will occur. Once participants complete the pre-test, intervention, and immediate post-test, they will not be re-contacted 3-4 weeks later for a follow up post-test. Newly enrolled participants who complete one wave of data collection will also be compensated with a total of \$50 in e-gift cards; just as their counterparts who were enrolled in two waves of data collection.

For participants randomly assigned to the pamphlet only condition, an opportunity to view the short film will be available upon submitting their anonymous responses to the post test survey.

6) Data and Specimen Banking*

N/A

7) Data Management

To maintain participants' privacy, identifying information will be safely maintained in a secured password protected file that only study team members will have access to. The study will be administered using Qualtrics survey software. All quantitative data will be analyzed using SPSS 24 and Mplus.

8) Risks to Subjects

There are no physical risks anticipated with participation in this study. It is possible that participants may experience some stress in completing the questionnaire, and/or some inconvenience in the time taken to participate in the two waves of this study. A breach of confidentiality is also a potential risk, but measures will be taken to minimize that risk (please see confidentiality section below). Due to anticipating minimal risks, this study will not assess adverse effects.

9) Potential Benefits to Subjects

No direct benefit can be promised to you from being in this study.

10) Compensation

Participants in the PSA pre-test will be compensated \$25. Light refreshments or lunch will be served during PSA pre-test sessions. Currently enrolled participants in the main study will be compensated with virtual Amazon gift cards oppose to cash. Participants will receive \$30 for the first part of the main study and \$20 for the follow up questionnaire of

Version 10.5.2018 Page 5 of 11

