Additionally, as a form of recruitment for the main study, HIV servicing agencies across the Southern U.S. will be asked to share the virtual flyer on their Facebook pages. Lastly, using data from the CDC and GIS mapping, researchers will employ targeted Facebook recruitment using Facebook ads. Ads will be run in Southern U.S. states that are identified to have a moderate to high prevalence of HIV. Further, ads will be displayed among Facebook users in the selected states, who meet the study criteria.

Lastly, a Qualtrics panel will be used for recruitment. According to Qualtrics, "A market research panel, also known as an online sample, is a group of people recruited to respond to a survey. They are typically chosen from a pre-arranged pool of respondents who've agreed to be contacted by a market research service in order to respond to surveys." Employing the

Version 10.5.2018 Page 7 of 11

study inclusion/exclusion criteria, Qualtrics panel, recruits willing participants for study participation. Participants recruited via the Qualtrics panel will be compensated directly via Qualtrics. They will compensated the amount agreed upon by their provider. However, compensation will be at least \$50 in gift cards for their participation.

Eligibility is restricted to black women ages 18-50, living in the Southern U.S., that have been clinically diagnosed with HIV/AIDS, who can read and comprehend English.

Note that participation is voluntary, and all participants will have the right to choose whether to participate or not.

16) Local Number of Subjects

The first iteration of the study enrolled 50 participants. For the current iteration of the study up to 30 phase one participants will be enrolled for the PSA pre-test. Up to 400 study participants will be enrolled for the main study. Altogether, this study will enroll up to 500 participants.

17) Confidentiality

The pre-test survey for the PSA will not ask any personally-identifying information. The pre- and post-film surveys and follow up-questionnaire will not ask any personally-identifying information. However, we will collect contact details (email address) of participants in order to schedule the second wave of the investigation and compensate participants. Contact details will be stored separately from the survey responses and will be deleted after data collection is complete. No personally identifiable information will be included in any written reports of the results.

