Statistical Analysis Plan

Investigating the Effectiveness of an Entertainment Education Short Film for Internalized HIV

Stigma Reduction, Intimate Partner Status Disclosure Intentions, and Antiretroviral Medical

Adherence Intentions: A Randomized Controlled Trial Among Black Women Living with HIV

in the Southern U.S.

ClinicalTrials.Gov Identifier: NCT03898063

February 15, 2021

Introduction: Purpose of the Statistical Analysis Plan (SAP)

The purpose of this Statistical Analysis Plan (SAP) is to detail the study objectives, study hypotheses and research questions, as well as the primary outcome measures and data analyses.

Study Overview

This randomized controlled trial was conducted among Black women living with HIV in the Southern U.S. between the ages of 18 and 50. The study examined the efficacy of a short entertainment education (EE) narrative in comparison to a standard brochure for primarily improving the following: HIV status disclosure intentions, internalized HIV-related stigma, and antiretroviral medical adherence. Once consented, all participants completed a pre-test survey. Upon completing the pre-test, using the randomization feature in Qualtrics, participants were randomly assigned to one of two study arms: 1) EE narrative or 2) Brochure. After viewing the EE stimulus or the brochure, participants immediately completed a post-test survey. The primary aim of the study is listed below.

Aim 1. To investigate the effectiveness of an EE intervention for decreasing internalized HIV-stigma and increasing HIV status disclosure intentions and medical adherence intentions among Black women living with HIV in the Southern U.S.

The hypotheses guiding this research study included the following:

H_{1a-c}: Participants in the EE condition will report: a) lower levels of internalized stigma; b) higher levels of disclosure intentions; c) higher levels of medical adherence intentions.

Data Collection Plan

Participants will be recruited via two primary methods. Firstly, Facebook advertisements will be deployed to recruit participants who meet the inclusion criteria. Secondly, participants will be recruited via a Qualtrics panel.

Statistical Methods

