An Analysis of Covariance (ANCOVA) will be used to control for the influence of age on the relationships of interest. This analysis will determine if there is a statistically significant difference between the treatment arm (90 DAYS film) and the control arm (Brochure) on the following primary variables: internalized stigma, intentions to disclose, and intentions for medical adherence. The analyses will be conducted using SPSS version 24.

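### The protocol rules out assessing adverse effects, and no distress measure is described, so distress could not be compared between the film and brochure arms

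*Protocol*

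**What the plan says.** Protocol section 8 (Risks to Subjects) expects no physical risk. It lists three other possibilities: stress, inconvenience from the time taken, and a breach of confidentiality. On stress it says: "It is possible that participants may experience some stress in completing the questionnaire". The section ends with a rule: "Due to anticipating minimal risks, this study will not assess adverse effects".

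Section 5 (Procedures Involved) sets the timing. Women complete a pre-test, are randomised to film or brochure, and then: "Upon completing one of the interventions, participants will be asked to immediately complete the post-test questionnaire". Of newly enrolled women it says "they will not be re-contacted 3-4 weeks later for a follow up post-test"; only the three already enrolled keep a second questionnaire.

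The SAP (Statistical Methods) compares the arms on "internalized stigma, intentions to disclose, and intentions for medical adherence". Its hypotheses (Study Overview) all point towards benefit: "Participants in the EE condition will report: a) lower levels of internalized stigma; b) higher levels of disclosure intentions; c) higher levels of medical adherence" (the last item concerns what women intend, not measured behaviour).

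**The concern.** The decision not to assess adverse effects is a stated rule, not a gap in the write-up. The reason given is that risk is expected to be minimal, and the rule removes the data that could check that expectation. For nearly all participants the immediate post-test is the only scheduled contact after exposure, so a distress question left out there has no later planned place.

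The protocol's objective is to learn whether and how the film can serve as an intervention. A reader of a positive result on stigma and intentions may reasonably ask whether viewers found the film harder to sit through than the brochure. Under the plan as described, the report would have no distress data with which to answer, even though a randomised comparison at the post-test would be easy to obtain.

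**Working it through.** The point rests on text. The documents give no harm rate, alpha or power, so there is no stated figure to reproduce.

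**Step 1: what is named and what is measured.**

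| Item | Where | Measured by arm? |
|---|---|---|
| Stress from the questionnaire | Protocol section 8 | No measure described |
| Distress from the film or brochure | Not named in the documents | No measure described |
| Internalized stigma | SAP, Statistical Methods | Yes; worsening would be visible |
| Disclosure and adherence intentions | SAP, Statistical Methods | Yes; worsening would be visible |

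Section 5 also lists the content of the one-month questionnaire for the three women already enrolled: attitudes, intentions, behaviour and stigma. No harm item is listed there. The Facebook recruitment paragraph of section 5 still describes a later reminder and follow-up survey. Even if that applied, no harm item is described for it.

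**Step 2: is the comparison clean at the post-test?** Assignment follows the pre-test, and women in the brochure arm are offered the film only after submitting their post-test. Answers to an identical item in both arms would therefore be uncontaminated by that later offer. Women who leave the survey before the item would be missed.

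**Step 3: what an added item could show (scale only).** Inputs:
- Protocol section 16: "Up to 400 study participants will be enrolled for the main study". This is a ceiling.
- SAP, Study Overview: "participants were randomly assigned to one of two study arms". No allocation ratio is stated, so I assume 1:1, giving 400 / 2 = 200 per arm.
- Distress rates are assumed.

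Upper limit with no reports in one arm (one-sided 95%): 1 − 0.05^(1/n).
- n = 200: 1 − 0.05^(1/200) = 0.0149, about 1.5%.
- n = 100 (half the ceiling): 1 − 0.05^(1/100) = 0.0295, about 3.0%.

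Half-width of the 95% interval for the difference, with the same rate p in both arms: 1.96 × √(2p(1 − p)/n).
- p = 10%, n = 200: 1.96 × √(2 × 0.10 × 0.90 / 200) = 1.96 × 0.030 = 0.0588, about 5.9 points.
- p = 5%, n = 200: 1.96 × √(2 × 0.05 × 0.95 / 200) = 1.96 × 0.0218 = 0.0427, about 4.3 points.
- p = 20%, n = 200: 1.96 × √(2 × 0.20 × 0.80 / 200) = 1.96 × 0.040 = 0.0784, about 7.8 points.
- p = 10%, n = 100: 1.96 × √(2 × 0.10 × 0.90 / 100) = 1.96 × 0.0424 = 0.0832, about 8.3 points.

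These figures describe what the proposed item would deliver among women who complete the post-test. They do not measure the size of any harm.

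**The case against.** The strongest reply is that this is a reasoned choice. The study is a single online session comparing a film with a brochure, the protocol presumes minimal risk (section 11 as well as section 8), and the SAP's one listed aim concerns stigma and intentions. No safety claim is planned and the primary comparison is not biased. All of that stands, and it is why the point is an improvement and not a fault in the main analysis.

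A reader might infer that the protocol foresees women being upset by the film and then declines to look. The text does not support that. It ties stress to the questionnaire, which both arms complete. Its background mentions emotional mechanisms of persuasion, but also suggests that entertainment education may be a less threatening way to open such conversations. Distress caused by the film is my inference.

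A reader might also infer that the trial can see only benefit. That goes too far. The SAP looks for a difference between arms and specifies no one-sided test, so worsening of stigma or intentions in the film arm would appear. What is missing is distress as a construct of its own.

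Finally, the measures guide mentioned in section 5 and a part of the protocol after the start of section 13 were not available to me. A distress-type item there cannot be excluded, although the rule in section 8 and the SAP's outcome list both point against one. Women also have the study team's contact details and may withdraw, so a complaint could arrive. No tabulation by arm is described, and with anonymous responses and separately stored contact details (sections 5 and 17) linking a complaint to an arm is barely feasible.

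**Conclusion.** The concern holds in a limited form. Section 8 names questionnaire stress as possible and rules out assessing adverse effects. No distress or harm measure is described in the text available or in the SAP's outcomes. The planned analysis would therefore give no comparison of distress by arm, and a report could not say whether the film was more, less or equally upsetting than the brochure. The documents do not show that the film is upsetting, and they do not plan a claim that it is safe.

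This is a cheap improvement whose downside is a slightly longer survey. The primary comparison stands. The illustrative precision (about 1.5% for 0 of 200 reports; about ±5.9 points at 10% in each arm) rests on equal allocation, full enrolment to the ceiling and an assumed rate, and covers post-test completers only.

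**What to change.** **If data collection is open.** Replace the closing sentence of section 8 with a rule along these lines: the immediate post-test will carry two separate items, identical in both arms and placed after the primary outcome scales, one asking about distress from the assigned material and one about distress from the survey questions. Two items are needed because a single combined question would mix a burden shared by both arms with an effect of the film.

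Add to the SAP: both items, and survey exits after randomisation, will be tabulated by arm with 95% confidence intervals and no hypothesis test. Exits matter because a woman upset enough to leave would never reach the items. They are only a crude signal, since women leave for other reasons too.

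**If data collection is closed.** The SAP's Study Overview is in the past tense while its recruitment and methods text is in the future tense, so the status is unclear. In that case tabulate exits by arm from the existing survey records, as far as partial responses were kept. State in the conclusions that adverse effects were not assessed and that no statement on the film's safety or acceptability relative to the brochure can be made.

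**Cost.** A short amendment, two extra survey items (a slightly longer questionnaire) and one descriptive table. Placing the items last keeps them from influencing the primary scales. With collection closed, the cost is one table and one sentence.

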Multiple strategies will be employed for participant recruitment. For the PSA pre-test phase, participants will be recruited by self-referral, word of mouth, or referred by a staff member or provider from the University of Miami, Jackson Memorial Hospital, including the HIV clinics, as well as other HIV service providers. More specifically, the research team will partner with Care Resource and AIDS Healthcare Foundation for participant referrals. Each of these agencies service our target population. As part of a memorandum of understanding, Care Resource will be compensated for their assistance with patient referrals for the study. Their referral process will include contacting qualified participants to inform them of the study, as well as referring interested patients within clinic to the study. AIDS Healthcare Foundation will inform patients within clinic of the study and refer them to the research team if they desire to participate. Dependent upon the study schedule, research team members maybe stationed at recruitment sites to immediately enroll participants. To maintain confidentiality throughout the recruitment process, the two-step approach will be employed. Firstly, potential participants may view the recruitment flyer or be referred by UM or JMH staff, or other HIV service providers, who will inform patients of the study, including the purpose of the study and participation criteria. Second, patients who express interest in participating will be referred to a research team member who will provide further information. Due to the sensitive nature of this study, should a patient decline to participate, they will not be referred to the research team. Should a participant agree to partake in the study, they will be provided consent forms from a study team member as well as the pre-questionnaire. If research staff are not onsite, interested participants will contact the identified study team member listed on the recruitment flyer. Researchers will partner with the Behavioral Registry Study at the University of Miami. This partnership will provide contact information for willing potential research participants that meet the inclusion criteria.

Additionally, as a form of recruitment for the main study, HIV servicing agencies across the Southern U.S. will be asked to share the virtual flyer on their Facebook pages. Lastly, using data from the CDC and GIS mapping, researchers will employ targeted Facebook recruitment using Facebook ads. Ads will be run in Southern U.S. states that are identified to have a moderate to high prevalence of HIV. Further, ads will be displayed among Facebook users in the selected states, who meet the study criteria.

Lastly, a Qualtrics panel will be used for recruitment. According to Qualtrics, "A market research panel, also known as an online sample, is a group of people recruited to respond to a survey. They are typically chosen from a pre-arranged pool of respondents who've agreed to be contacted by a market research service in order to respond to surveys." Employing the

Version 10.5.2018 Page 7 of 11

study inclusion/exclusion criteria, Qualtrics panel, recruits willing participants for study participation. Participants recruited via the Qualtrics panel will be compensated directly via Qualtrics. They will compensated the amount agreed upon by their provider. However, compensation will be at least \$50 in gift cards for their participation.

Eligibility is restricted to black women ages 18-50, living in the Southern U.S., that have been clinically diagnosed with HIV/AIDS, who can read and comprehend English.

Note that participation is voluntary, and all participants will have the right to choose whether to participate or not.

16) Local Number of Subjects

The first iteration of the study enrolled 50 participants. For the current iteration of the study up to 30 phase one participants will be enrolled for the PSA pre-test. Up to 400 study participants will be enrolled for the main study. Altogether, this study will enroll up to 500 participants.

17) Confidentiality

The pre-test survey for the PSA will not ask any personally-identifying information. The pre- and post-film surveys and follow up-questionnaire will not ask any personally-identifying information. However, we will collect contact details (email address) of participants in order to schedule the second wave of the investigation and compensate participants. Contact details will be stored separately from the survey responses and will be deleted after data collection is complete. No personally identifiable information will be included in any written reports of the results.

18) Provisions to Protect the Privacy Interests of Subjects

Only authorized members of the study team will have access to the data. Lastly, an assigned research team member will contact participants to provide a reminder of the follow up survey. Participants will be individually contacted and compensated via email.

19) Consent Process

The consent process for the PSA pre-test will be as follows. Firstly, clinic providers and staff will inform patients of the study, including the purpose of the study and participation criteria. Second, patients who express interest in participating will be provided contact information for a research team member who will be able to provide further information on the study. Due to the sensitive nature of this study, should a patient decline to participate, they will not be referred to the research team. The study team member will provide the interested participant with the consent forms to read and ask any questions to their full satisfaction and understanding. After the consent forms are signed and copies given to the participant, the study team member will administer the pre-questionnaire.

Version 10.5.2018 Page 8 of 11

Due to the main study being conducted via the Qualtrics survey software, participants will be provided a thorough consent form. Should the participant agree to participate, their consent will be determined based upon their decision to select "next" and complete the study. Moreover, all participants for the PSA manipulation check and main study will be informed of their right to remove themselves from the study or withdraw their responses at any time without penalty. Respondents will also have the contact information of the study team in case they have questions.

20) Process to Document Consent in Writing

For both the PSA manipulation check and the main study, participants will document their consent by completing the study questionnaires. Therefore, while informed consent will transpire, signed consent will not. This will reduce the amount of personal identifiable information reported.

Version 10.5.2018 Page 9 of 11

References

- AIDSVu. (n.d.) Miami (Miami-Dade County) Highlights. Retrieved from: https://aidsvu.org/state/florida/miami/
- Centers for Disease Control and Prevention. (2017). *Living with HIV*. Retrieved from: https://www.cdc.gov/hiv/basics/livingwithhiv/index.html
